Appendix B. Analysis of Binary Endpoints

The point estimate of the response rate for each treatment group is calculated as $\hat{p} = \frac{k}{N}$ where k denotes the number of responders in the treatment group and N denotes the total number of subjects in the treatment group. The corresponding 95% CI is based on normal approximation, that is $\hat{p} \pm Z_{0.975} \sqrt{\frac{1}{N} \hat{p}(1 - \hat{p})}$, where $Z_{0.975}$ denotes the 97.5% quantile of the standard normal distribution. This is implemented by obtaining the Wald asymptotic confidence limits using the SAS procedure PROC FREQ with the BINOMIAL option. The SAS code example is as follows:

```
proc freq data=TESTData1;
  by TRTP;
  tables RESP / binomial (level="1") alpha=0.05;
  weight COUNT/zero;
  output out=CI (keep= L_BIN U_BIN) binomial;
run;
```

Note: The input dataset is cell count data, with variable RESP denoting response status ("1" as responder and "0" as non-responder) and variable COUNT denoting the number of subjects with the corresponding response status.

The treatment difference is calculated as $\hat{p}_1 - \hat{p}_2$ and the corresponding 95% CI for the treatment difference is based on normal approximation, that is $\hat{p}_1 - \hat{p}_2 \pm Z_{0.975} \sqrt{\frac{1}{N_1} \hat{p}_1(1 - \hat{p}_1) + \frac{1}{N_2} \hat{p}_2(1 - \hat{p}_2)}$. This is implemented by obtaining the Wald asymptotic confidence limits using the SAS procedure PROC FREQ with the RISKDIFF option. The SAS code example is as follows:

```
proc freq data=TESTData1;
  tables TRTP*RESP / riskdiff alpha=0.05;
  weight COUNT/zeros;
```

```
where TRTP in ('PLACEBO', 'UPA 15MG');
output out=diff(keep= _RDIF1_ L_RDIF1 U_RDIF1) riskdiff1;
run;
```

Note: The input dataset is cell count data, with variable RESP denoting response status ("1" as responder and "0" as non-responder) and variable COUNT denoting the number of subjects with the corresponding response status. TRTP denotes the treatment group.

The p-value for the treatment comparison is based on the Cochran-Mantel-Haenszel (CMH) test adjusting for stratification factor. This is implemented using the SAS procedure PROC FREQ with the CMH option. The p-value from the "general association statistic" is used. The SAS code example is as follows:

```
proc freq data=TESTData3;
tables STRATA*TRTP*RESP_VALUE / cmh;
run;
```

Note: The input dataset is subject-level data, with variable RESP _ VALUE denoting the subject's response status ("1" as responder and "0" as non-responder). TRTP denotes the treatment group and STRATA denotes the strata for a given subject.

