4.2 Overall Study Design and Plan

This is a Phase 3 multicenter study that includes two periods. Period 1 is a 12-week, randomized, double-blind, parallel-group, placebo-controlled period designed to compare

the safety and efficacy of upadacitinib 15 mg QD versus placebo for the treatment of signs and symptoms of subjects with moderately to severely active RA from China, Brazil, and South Korea who are on a stable dose of csDMARDs and have an inadequate response to csDMARDs. Period 2 is an open-label 52-week extension period to evaluate the long-term safety, tolerability, and efficacy of upadacitinib 15 mg QD in subjects from China, Brazil, and South Korea who have completed Period 1.

The study is designed to enroll approximately 322 subjects at approximately 50 study centers in China, Brazil and South Korea to meet scientific and regulatory objectives without enrolling an undue number of subjects in alignment with ethical considerations. Therefore, if the target number of subjects has been enrolled, there is a possibility that additional subjects in screening will not be enrolled.

The study duration will include a 35-day screening period; a 12-week randomized, double-blind, parallel-group, placebo-controlled treatment period (Period 1); an open-label 52-week extension period (Period 2); and a 30-day follow-up period (visit or call).

Subjects who meet eligibility criteria will be randomized in a 1:1 ratio to one of two treatment groups. It is expected that approximately 222 subjects will enter the study from China and 100 subjects from other countries including Brazil and South Korea:

- Group 1: upadacitinib 15 mg QD (Period 1) → upadacitinib 15 mg QD (Period 2)
- Group 2: Placebo (Period 1) → upadacitinib 15 mg QD (Period 2)

Randomization will be stratified by country.

Subjects must have been on a stable dose of csDMARD(s) for ≥ 4 weeks prior to the first dose of study drug and must remain on a stable dose until Week 24; the csDMARD dose may be decreased only for safety reasons. At Week 24, if a subject fails to meet the Low Disease Activity (LDA) criterion (LDA defined as CDAI ≤ 10) the investigator should adjust the subject's background RA therapies. Starting at Week 24 (after Week 24

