4.3 Sample Size

The planned total sample size of 322 for this study provides over 90% power for a 21.7% difference in ACR20 response rate at Week 12 (assuming a placebo ACR20 response rate of 36.7%), at two-sided significance level of 0.05 and accounting for a 10% dropout rate. This sample size will also provide at least 90% power for most of the key secondary endpoints, including change from baseline in DAS28 (CRP), ACR50 response rate, LDA and CR based on DAS28 (CRP), and SF-36 PCS, at two-sided significance level of 0.05 and accounting for a 10% dropout rate.

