9.2.1 Primary Efficacy Analysis

The primary endpoint is ACR20 response at Week 12. Analysis of the primary endpoint will be conducted on the FAS based on randomized treatment groups (upadacitinib 15 mg QD and the placebo group). Point estimate and 95% CI using normal approximation will be provided for the response rate for each randomized treatment group. Comparison of the primary endpoint will be made between the upadacitinib group and placebo group using the Cochran-Mantel-Haenszel test adjusting for stratification factor country. Point estimate, 95% CI using normal approximation and p-value for the treatment comparison will be presented. P-value is constructed using the Cochran-Mantel-Haenszel test. For the primary analysis, non-responder imputation (NRI) will be used.

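### The binary-endpoint differences and confidence intervals ignore country while the p-values beside them are stratified by it: a small inconsistency, cheap to remove

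*SAP*

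**What the plan says.** Subjects are "randomized in a 1:1 ratio to one of two treatment groups", with randomisation stratified by country (SAP 4.2; Protocol 5.1 and 8.3).

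For the primary endpoint, SAP 9.2.1 promises this output: "Point estimate, 95% CI using normal approximation and p-value for the treatment comparison will be presented". It then assigns only the p-value to the CMH test. Appendix B shows how each part is produced:

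- p-value: "tables STRATA*TRTP*RESP_VALUE / cmh", which carries the stratum variable.
- Difference and interval: "tables TRTP*RESP / riskdiff alpha=0.05", which does not. The formula given is the crude difference with a Wald interval and unpooled variance.

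The same appendix serves ranked endpoints 4 to 6 (two low-disease-activity definitions and clinical remission) and the remaining binary endpoints. For those, SAP 9.2.4 and Table 7 are worded so that the estimate and interval also appear to come from the country-adjusted CMH analysis. Appendix B shows that they do not.

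The continuous ranked endpoints (1 to 3) take estimate, interval and p-value from one country-adjusted model (SAP 9.2.3, Appendix C). Protocol 8.1.4.1.1 names the CMH test and gives no interval method.

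**The concern.** The primary result will be reported as a difference, an interval and a p-value on one line, and a reader will assume that they belong together. Here the p-value conditions on country and the interval does not. If response rates differ between countries, the pooled variance includes between-country variation that stratified randomisation has already balanced across arms, so the interval is longer than the design requires. In a borderline trial the interval could include zero beside a significant p-value, or the reverse.

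The plan is also uneven within a single testing sequence, because three ranked endpoints are country-adjusted throughout while the primary and the other three are adjusted only in the p-value.

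**Working it through.** **Inputs.** From SAP 4.3: total 322 (161 per arm), placebo rate 36.7%, difference 21.7 points (so 58.4% on upadacitinib), two-sided 0.05, 10% dropout. From Protocol 5.1: 111 per arm from China, hence 50 per arm elsewhere. Assumed, because the documents are silent: the 50 split 25/25 between two countries, a constant treatment difference, and a placebo-rate gap g between China and the rest, with the overall placebo rate held near 36.7%.

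**1. The plan's own figure.** SAP 4.3 states: "The planned total sample size of 322 for this study provides over 90% power for a 21.7% difference in ACR20 response rate". After dropout, 322 × 0.9 / 2 ≈ 145 per arm. The pooled-variance normal approximation gives 96.3% power (97.6% at 161 per arm). The statement is reproduced, and it concerns the test rather than the interval.

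**2. The SAP interval at the design rates.** Non-responder imputation keeps all 161 per arm in the denominator.

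SE = √[(0.584 × 0.416 + 0.367 × 0.633)/161] = √(0.4753/161) = 0.0543

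Half-width = 1.96 × 0.0543 = 10.65 points, so the expected interval is about 11.1 to 32.3.

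**3. Effect of stratifying on width.** With exact 1:1 allocation in each country, the Mantel-Haenszel difference equals the crude one. Only the variance changes, losing the between-country part. Per arm that part is (111/161)(50/161)g² = 0.2141g², so

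stratified SE / pooled SE = √[1 − 2 × 0.2141g²/0.4753].

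For g = 0.30 this is √(1 − 0.0811) = 0.959. The excess width of the SAP interval is 1/0.959 − 1 ≈ 4.3%.

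**4. Agreement with CMH.** Results below are from 200,000 simulated trials per scenario. Disagreement means that the pooled interval and CMH fall on opposite sides of significance.

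| Country gap | SAP half-width | Stratified half-width | SAP excess | Disagree, 21.7-point effect | Disagree, 12-point effect |
|---|---|---|---|---|---|
| 0 | 10.65 | 10.65 | 0% | 0.00% | 0.2% |
| 10 points | 10.65 | 10.60 | 0.5% | 0.00% | 0.25% |
| 20 points | 10.65 | 10.46 | 1.9% | 0.07% | 1.2% |
| 30 points | 10.65 | 10.21 | 4.3% | 0.34% | 3.7% |

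Coverage of the pooled interval ranged from 94.8% to 95.9%. With placebo rates of 25/65/45% (China and two others) the excess is about 5%, and disagreement is about 0.5% at 21.7 points and 3.9% at 12. If every country outside China differed by 40 points, the formula gives a ratio of 0.925, an 8% excess.

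**5. A constructed example.** Responders out of 111/25/25 are 44/19/15 on upadacitinib and 33/17/11 on placebo.

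- Crude difference: (78 − 61)/161 = 10.56 points, SE 0.0549. SAP interval −0.2 to 21.3, which includes zero.
- CMH: Σ(x₁ − m/2) = 8.5, where m is the stratum's total responders. The variance is 12.63 + 2.57 + 3.18 = 18.39, and χ² = 72.25/18.39 = 3.93, p = 0.047.
- Mantel-Haenszel with Sato variance, balanced strata: Var = [d·ΣP + ΣQ]/(Σw)². Here P = (x₂ − x₁)/4, Q = [x₁(n − x₂) + x₂(n − x₁)]/(4n) and w = n/2, with n per arm in the stratum. ΣP = −4.25, ΣQ = 12.71 + 2.54 + 3.20 = 18.45 and Σw = 80.5. Var = (18.45 − 0.45)/6480.25 = 0.00278, SE 0.0527, interval 0.2 to 20.9, which excludes zero and agrees with CMH.

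The reverse can happen too. Responders 84/12/12 v 59/16/16 give a pooled interval of 0.01 to 21.1 with CMH p = 0.052.

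**6. Which stratified variance.** Summing within-stratum Wald variances is biased low with 25 per arm. With no country gap its mean SE is 0.0538 against 0.0542. It disagrees with CMH at 12 points in 0.6%, 1.1%, 1.7% and 0.9% of trials for gaps of 0, 10, 20 and 30 points. The Sato variance matches the pooled interval when there is no gap (0.2% disagreement, 95.0% coverage). It costs at most 0.2 percentage points of disagreement at small gaps, and at large gaps cuts it from about 3.8% to 0.4%.

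**The case against.** The strongest reply is that nothing decisive depends on this interval. The step-down procedure in SAP 9.2.5 runs on significance, and the p-values come from CMH. Appendix B states both formulas openly, and the pooled interval covers at its nominal rate. With 1:1 allocation within country the crude and weighted differences are practically equal. All of that stands.

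It also stands that the excess width is conditional. A reader might infer that the interval is definitely wider than it needs to be. The documents do not support that, because they give no country-specific ACR20 rates, and with equal rates there is no excess at all. A reader might likewise take the 4% disagreement as typical. It needs both very large country gaps and an effect of about 12 points, whereas the plan assumes 21.7.

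A further objection is that stratifying can worsen agreement with CMH, because part of the mismatch comes from null versus unpooled variance. That is correct for a plain sum of within-stratum Wald variances at small and moderate gaps (step 6). It does not carry over to the Sato variance to any material extent.

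**Conclusion.** The mismatch is real and documented: a country-stratified test stands beside a country-blind estimate and interval, under country-stratified randomisation. Its consequences are small. The interval is valid and at worst somewhat conservative. The excess is 0% with no country gap, under 1% at about 10 points and roughly 4 to 5% for the large-gap scenarios (8% only if all other countries differ from China by 40 points). Disagreement with CMH is at most about 0.5% of trials at the planned effect, and about 4% at a borderline 12-point effect with very large gaps.

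These sizes rest on assumed country rates, the assumed 25/25 split outside China and a constant treatment difference. It would be wrong to infer that the primary conclusion, type I error, power or the testing order is at risk, or that the estimate is biased. The case for change is coherence within the plan and clearer SAP wording, with a possible small gain in precision.

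**What to change.** For ACR20 at Week 12, ranked endpoints 4 to 6 and the other binary endpoints, report the Mantel-Haenszel country-weighted common risk difference with its stratified 95% interval beside the CMH p-value. Specify the Sato variance by name, not a sum of within-stratum Wald variances. Keep the crude difference as descriptive. Align SAP 9.2.1, 9.2.4, Table 7 and Appendix B so that each says the same about where the estimate, interval and p-value come from.

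The cost is one changed analysis call and some SAP text. The test, sample size and data collection do not change. It should be settled before the Period 1 database lock, because choosing between two intervals after unblinding would be post hoc.

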Appendix C. Analysis of Continuous Endpoints using Mixed Effect Model Repeat Measurement (MMRM)

The repeated measure analysis will be conducted using mixed model including observed data at all visits. For the MMRM analysis, data collected after premature discontinuation of study drug will be excluded. The mixed model includes the categorical fixed effects of treatment, visit and treatment-by-visit interaction, main stratification factors at randomization and the continuous fixed covariates of baseline measurement. An unstructured variance covariance matrix will be used. The parameter estimations are based on the assumption of data being missing at random and using the method of restricted maximum likelihood (REML).

The MMRM is implemented using the SAS procedure PROC MIXED. The LSMEANS statement provides the least-squares means and corresponding 95% CIs for each treatment group at each visit, as well as the least-squares means, corresponding 95% CIs and p-values for treatment comparisons at each visit. The SAS code example is as follows:

```
proc mixed data=CData;
  class TRTP AVISIT STRATA USUBJID;
  model CHG = TRTP AVISIT BASE STRATA TRTP*AVISIT / DDFM=kr htype = 3;
  repeated AVISIT / subject = USUBJID type=un;
  lsmeans TRTP*AVISIT/ c1 diff;
  ods output lsmeans=lsmean_output;
run;
```

Note: The input dataset is per subject per visit. USUBJID is the unique subject number, TRTP denotes the treatment group, STRATA denotes the strata, and AVISIT denotes the visit. CHG denotes the change from baseline value and BASE denotes the baseline value.

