9.1.2 Definition of Missing Data Imputation

Non-Responder Imputation (NRI) Approach

The NRI approach will categorize any subject who has missing value for categorical variables at a specific visit as non-responder for that visit. In addition, subjects who prematurely discontinue from study drug will be considered as non-responders for all subsequent visits after discontinuation.

Observed Cases (OC)

The OC analysis will not impute values for missing evaluations, and thus a subject who does not have an evaluation on a scheduled visit will be excluded from the OC analysis for that visit. In addition, the OC will not use values after premature discontinuation of study drug. This sensitivity analysis will only be applied to the analysis in Period 1.

As Observed (AO)

The AO analysis will not impute values for missing evaluations, and thus a subject who does not have an evaluation on a scheduled visit will be excluded from the AO analysis for that visit. Regardless of treatment switching or premature discontinuation of study drug, all observed data will be used in the analysis. The AO analysis will be applied to long-term efficacy analysis.

Mixed Effect Model Repeat Measurement (MMRM)

The repeated measure analysis will be conducted using mixed model including observed measurements at all visits. The mixed model includes the categorical fixed effects of treatment, visit and treatment-by-visit interaction, main stratification factors at randomization, and the continuous fixed covariates of baseline measurement. An unstructured variance covariance matrix will be used. The parameter estimations are based on the assumption of data being missing at random and using the method of restrictive maximum likelihood (REML). The missing at random assumption is considered reasonable given the high placebo response rate typically seen in RA trials. Additionally, in RA trials, the proportion of discontinuation is relatively small (10 – 15% only) and the rate of discontinuation due to lack of efficacy is generally low (< 5%).

Multiple Imputation (MI)

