9.2.3 Key Secondary Efficacy Analyses

Ranked key secondary endpoints (at Week 12) are:

1. Change from baseline in DAS28 (CRP);
2. Change from baseline in HAQ-DI;
3. Change from baseline in Short Form-36 (SF-36) Physical Component Score (PCS);
4. Proportion of subjects achieving LDA based on DAS28 (CRP) ≤ 3.2 ;
5. Proportion of subjects achieving Clinical remission (CR) based on DAS28 (CRP);
6. Proportion of subjects achieving LDA based on CDAI ≤ 10 ;

Other key secondary endpoints (at Week 12) are:

1. ACR50 response rate;
2. ACR70 response rate;
3. ACR20 response rate at Week 1.

For binary endpoints, frequencies and percentages will be reported for each randomized treatment group. Similar analyses as for the primary endpoint will be conducted.

For the major RA continuous endpoints DAS28 and HAQ-DI change from baseline, statistical inference will be conducted using analysis of covariance (ANCOVA) coupled with MI for missing data handling. Specifically, the ANCOVA model will include treatment as the fixed factor, and the corresponding baseline value and the stratification factor country as the covariates. For other continuous endpoints, statistical inference will be conducted using the MMRM model as described in Section 9.1.2, with the main stratification factor being country. From both the MI and MMRM analyses, the LS mean and 95% CI will be reported for each randomized treatment group; the LS mean treatment difference and associated 95% CI and p-value will be reported comparing upadacitinib group with the placebo group.

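### The SAP's MMRM forces one baseline slope on all visits, which can cost a little Week 12 precision; a baseline-by-visit term would be a nearly free improvement

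*SAP*

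**What the plan says.** SAP 9.1.2 describes the model in words: "The mixed model includes the categorical fixed effects of treatment, visit and treatment-by-visit interaction", then "main stratification factors at randomization, and the continuous fixed covariates of baseline measurement". It adds: "An unstructured variance covariance matrix will be used". Appendix C gives matching code: the MODEL statement "model CHG = TRTP AVISIT BASE STRATA TRTP*AVISIT / DDFM=kr htype = 3" and the covariance statement "repeated AVISIT / subject = USUBJID type=un". SAP 9.2.4 and Table 7 list the same terms. No place has a baseline-by-visit term, so text, table and code agree.

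The model reaches these endpoints:
- **Ranked.** SAP 9.2.3 ranks "Change from baseline in Short Form-36 (SF-36) Physical Component Score" third. For DAS28 and HAQ-DI, ranks 1 and 2, "statistical inference will be conducted using analysis of covariance (ANCOVA) coupled with MI for missing data handling". For the rest, "For other continuous endpoints, statistical inference will be conducted using the MMRM model as described in Section 9.1.2". Ranks 4 to 6 are binary, so SF-36 PCS is the only ranked endpoint tested by MMRM. It has two post-baseline visits in Period 1, Weeks 4 and 12 (SAP 9.4.13 and Table 3).
- **Unranked.** SAP 9.2.4 applies the model to the additional continuous endpoints. The ACR components and the indices built from them have five post-baseline visits: Weeks 1, 2, 4, 8 and 12 (SAP Table 1).

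**The concern.** The model lets treatment effect, variance and correlation vary by visit, but not the effect of baseline. No reason is given for constraining only that term.

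For a change score, the slope on baseline depends on how strongly the visit value still correlates with baseline. If that correlation falls over follow-up, the slope steepens. A single slope is then a compromise, and it may sit close to the early visits. Week 12, the visit on which the ranked test is made, is then left with baseline-related variation that the model could have removed. What is at stake is the width of the Week 12 intervals and a little power, first for SF-36 PCS because it is ranked.

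**Working it through.** **1. The plan's own figures.** SAP 4.3 states over 90% power for ACR20 with 322 subjects, 36.7% against 36.7 + 21.7 = 58.4%, two-sided 0.05 and 10% dropout. Per arm, n = 161 × 0.9 = 144.9, and the pooled rate is 0.4755.

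z = [0.217 × √144.9 − 1.96 × √(2 × 0.4755 × 0.5245)] / √(0.367 × 0.633 + 0.584 × 0.416) = (2.612 − 1.384) / 0.689 = 1.78, so power is 96.3%. The statement holds. The same section claims at least 90% for SF-36 PCS but gives no effect size or SD, so that figure cannot be reproduced.

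**2. Formula.** Let b_v be the true slope of change on baseline at visit v:

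b_v = ρ_v × SD_v / SD_0 − 1

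Let S be the covariance of the visits given baseline, and s12² its Week 12 entry. With an unstructured covariance the common slope converges to

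β = 1′S⁻¹b / 1′S⁻¹1

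With complete data, the Week 12 SE relative to the model with visit-specific slopes is

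√[1 + (b12 − β)² × var(BASE) / s12²]

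With two visits and residual covariance c, the weights are proportional to s12² − c for Week 4 and s4² − c for Week 12.

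**3. SF-36 PCS, two visits.** All inputs are assumptions: baseline SD 7.5, so var(BASE) = 56.25.

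| | Moderate | Larger |
|---|---|---|
| SD at Weeks 4, 12 | 8, 8.5 | 8, 9 |
| Correlation with baseline at Weeks 4, 12 | 0.65, 0.55 | 0.70, 0.50 |
| Correlation of Week 4 with Week 12 | 0.7 | 0.8 |
| b4, b12 | −0.307, −0.377 | −0.253, −0.400 |
| s4², s12², c | 36.96, 50.39, 23.29 | 32.64, 60.75, 32.40 |
| Weights, Weeks 4 and 12 | 27.10, 13.67 | 28.35, 0.24 |
| β | −0.330 | −0.255 |
| SE ratio | √(1 + 0.0465² × 56.25 / 50.39) = 1.001 | √(1 + 0.1454² × 56.25 / 60.75) = 1.010 |

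The formula was also run over 405 assumed sets: follow-up SD 7.5–9, baseline correlation 0.5–0.7 at Week 4 falling by 0–0.20 by Week 12, and Week 4–12 correlation 0.6–0.8. SE inflation had median 0.2%, 90th percentile 0.9% and maximum 2.1%.

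In power terms, a test at 90% has 1.960 + 1.282 = 3.242 standard errors. A 2% larger SE gives 3.242 / 1.02 − 1.960 = 1.218, or 88.8%. A 1% larger SE gives 89.4%.

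**4. Five visits, unranked endpoints.** These inputs are also assumed.
- With baseline correlation falling from 0.70 to 0.55, inflation is 0.1–0.6%.
- With a fall from 0.6–0.8 at Week 1 to 0.3–0.5 at Week 12, it is 1.1–3.5%.
- With steep slopes, −0.10 rising to −0.60, a simulation gave an SE 8.7% smaller with the interaction. That is 1 / (1 − 0.087) = 1.095, or 9.5% inflation without it.

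The variances matter as much as the slopes. Take the steep slopes in equal steps, residual correlation 0.6 and var(BASE) = 1. With residual SD 1 at every visit, β is the mean slope, −0.35, and the ratio is √(1 + 0.25²) = 1.031. With residual SDs 0.7, 0.8, 0.9, 1.0 and 1.1, β is −0.123 and the ratio is √(1 + 0.477² / 1.21) = 1.090.

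**5. Are the standard errors right?** REML simulations used 322 subjects, country as a factor, Weeks 4 and 12, about 10% missing at Week 12 and 2,000 runs per scenario, with Wald tests in place of Kenward-Roger. Over the two columns of step 3:

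| | SAP model | With BASE*AVISIT |
|---|---|---|
| Mean SE / empirical SD | 0.986–1.013 | 0.986–1.012 |
| Type I error | 4.5–5.35% | 4.6–5.3% |

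Coverage under the SAP model was 94.0–95.5%. With dropout unrelated to the data and a true difference of 2.8 points, mean SEs were 0.8216 against 0.8210 (moderate) and 0.9000 against 0.8916 (larger), in line with step 3. When slopes were equal, the two models coincided. In complete-data runs of 4,000 per scenario over six scenarios, including the steep five-visit case, the common-slope SE was 0.992–1.017 of its empirical SD.

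**6. Dropout.** Under a deliberately arm-specific missing-at-random mechanism, the SAP model was biased towards the null by 0.06 points (moderate) and 0.13 points (larger) against a true 2.8. With the interaction the bias was under 0.01. In the larger case power was 84.3% against 87.7%.

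**The case against.** A common baseline slope is a legitimate prespecified choice, stated the same way in text, table and code. Nothing is contradictory or irreproducible. For the one ranked endpoint it touches, the loss is trivial under every assumed set. The larger five-visit figures concern endpoints outside the step-down sequence of SAP 9.2.5, and they move with assumed slopes and variances that the documents do not supply. All of that stands, and it is why this is an optional improvement rather than an error.

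Two stronger readings are tempting, and neither is supported.
- **A reader might infer that the reported standard errors are wrong.** They are not. Treatment-by-visit is saturated and the Week 12 variance is estimated freely, so slope misfit goes into that variance. The SE then describes the estimator actually used, as step 5 shows. The intervals are valid, though wider than they need be when slopes differ.
- **A reader might infer that rank 3 is adjusted less well than its neighbours,** since ranks 1 and 2 use a Week 12 ANCOVA with its own slope. Rank 4 is tested by CMH on country alone, with no baseline covariate. The documents give nothing from which to compare the SE of that ANCOVA with this MMRM.

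The bias in step 6 arose only under a constructed dropout pattern that nothing in the documents predicts. It gives modest further support for the term and is not a finding against the plan.

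**Conclusion.** The constraint is certain; its cost depends on slopes that are not known. If the baseline slope is the same at every visit, nothing is lost. If it differs, Week 12 is adjusted less efficiently than it could be:
- SF-36 PCS: SE about 0–2% larger, at most about one power point at 90%. That bound covers the SE effect only, not the constructed dropout case.
- Unranked five-visit endpoints (CDAI, SDAI, DAS28(ESR), pain, global assessments): roughly 1–4% under moderate steepening, up to about 10% under steep slopes.

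The validity of the ranked test is not in question. The primary endpoint and ranks 1, 2, 4, 5 and 6 do not use this model for their tests and are unaffected. Every size above rests on assumed slopes, SDs and correlations.

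**What to change.** Before unblinding, add BASE*AVISIT to the MODEL statement in SAP Appendix C, and name the baseline-by-visit interaction in the model descriptions in 9.1.2, 9.2.4 and Table 7. SAP 9.2.3 refers to 9.1.2 and would follow.

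The cost is one degree of freedom per additional visit: one for SF-36 PCS and four for a five-visit endpoint, with 322 subjects planned. The timing matters because adding the term to a ranked test after unblinding would look data-driven.
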